At the first adaptive analysis, confirmation of the validity of the proportional odds assumption will be carried out in each subphenotype. This will be based on the observed distribution of the primary outcome ordinal scale in each treatment intervention compared to usual care. If the proportional odds assumption is not met, then alternative categorisations (i.e. grouping some categories in the ordinal scale together) will be explored. For all adaptive analysis we will examine the consistency of the unadjusted between-group treatment effect across the composite outcome elements (death and organ support free days) for each comparison within each subphenotype.

Very little missing data are expected for the primary outcome; we anticipate minimal loss to follow-up, and eCRFs will be designed so that recording of primary outcome data is mandatory. If the level of missingness does not exceed 5% then the missing data will be assumed to be ignorable, i.e. a complete case analysis will be carried out. If over 5% of outcome data are missing, then the missingness pattern and relationship to other variables will be explored and multiple imputation will be performed.

Statistical stopping triggers

The criteria for stopping recruitment to a treatment group within either subphenotype are based on the probability that the unadjusted odds ratio crosses a predefined value by a predetermined probability threshold. The initial triggers for stopping were identified through extensive simulations to optimise the trial operating characteristics and achieve an appropriate balance between the sample size needed, maximising the power to graduate treatments exceeding the minimal clinically important effect and minimising the chance of graduating treatments with no effect (type I error).

Stopping recruitment to a treatment within either subphenotype will be considered if any of the following conditions are met at any adaptive analysis:

- For efficacy if there is at least an 84% probability of the proportional odds ratio exceeding 1.1.
- For futility if there is at least a 78% probability of the proportional odds ratio falling below 1.075.

These are considered non-binding stopping rules as the DMC will also take into consideration information presented on other outcomes including safety and recruitment data.

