9.6 Primary Modelling Approach for Adaptive and Final Analysis

'Adaptive analyses' are those performed regularly to make decisions for changing the trial. 'Final analysis' will performed once an intervention arm has met a statistical trigger and the DMC have confirmed stopping.

The primary efficacy analyses will be based on single Bayesian proportional odds logistic regression models fitted for each subphenotype. The primary **adaptive analysis** will be **unadjusted** and the **final primary efficacy** analyses will be **adjusted** for minimisation covariates and other strong prognostic variables. For adaptive and final analyses the posterior distribution of the proportional odds ratio (POR) associated with each treatment (relative to usual care) will be estimated using Markov Chain Monte Carlo techniques and the mean and 95% credible interval reported, and for the adaptive analyses the probability of exceeding the relevant statistical triggers (see above in Statistical stopping triggers). POR>1 relative to usual care indicates a favourable treatment effect. We will also examine the treatment effect across both subphenotypes by combining the data across

Confidential Page 32 of 48

subphenotypes and using the same regression model, reporting the POR and 95% credible interval. Full details of the adaptive and final analyses will be specified in the corresponding SAPs.

The primary analysis will use neutral informative prior distribution on the treatment effect where the variance will be chosen to only make extreme results highly unlikely. Where external trial evidence is available on the effect of an intervention in a particular subphenotype, a sensitivity analysis will include this evidence in the analysis using an informative prior distribution. Unadjusted and adjusted treatment effects will be presented in all reports.

Secondary efficacy endpoints

Secondary efficacy outcomes will be summarised and tabulated and unadjusted treatment effects will be calculated at each adaptive analysis. Full model-based analyses will be performed only at the final analysis for each treatment intervention in each subphenotype (i.e. once recruitment to a treatment group within a subphenotype is stopped).

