Estimands for analysis of secondary efficacy endpoints will use the same treatment conditions, the same population, and intercurrent events and strategies to handle these, apart from the outcome 'Progression to invasive mechanical ventilation, extracorporeal membrane oxygenation or death' which will use the population consisting of those participants not intubated at baseline and the handling of mortality which will alter depending on the nature of the outcome and its interpretation in relation to death, and length of stay which will use the population who survived. The outcome variable and population-level summary measure will vary as appropriate for each endpoint. All secondary estimands will be specified in the SAP.

Treatment effects for final analysis will be estimated using a regression modelling approach in a Bayesian framework with vague priors. Adjustment for baseline values will be used where suitable.

Analysis of ordinal secondary outcomes (days free of vasopressor or respiratory support) will be as per the primary outcome. Analysis of binary outcomes at single time points will use logistic regression. Analysis of continuous outcomes will use linear regression.

Posterior mean contrasts (differences, odds ratios, incidence rate ratios) between treatment groups will be reported together with 95% credible intervals. Model assumptions will be examined using residual analysis including examination of graphical displays such as normal quantile plots.

Serious Adverse events

In addition to the information on safety provided by the adaptive analyses of the primary and secondary outcomes, cumulative data on SAEs will be presented to the Data Monitoring Committee on a regular basis.

As there is monitoring of important safety outcomes through primary and secondary outcomes (eg mortality, organ support), these events will not be recorded as SAEs as described above. All other SAEs will be tabulated by arm and compared between arms through calculation of incident rate ratios (IRR) and 95% credible intervals (CI).

Confidential Page 33 of 48

London

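### Posterior means of odds ratios and rate ratios under vague priors would give prior-driven values for sparse safety events; the effect on the primary odds ratio is small

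*Protocol*

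**What the plan says.** Three statements in Protocol section 9.6 matter.

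- **Secondary outcomes, prior:** "Treatment effects for final analysis will be estimated using a regression modelling approach in a Bayesian framework with vague priors". No scale is given for the vague prior.
- **Secondary outcomes, model and summary:** "Analysis of binary outcomes at single time points will use logistic regression", and "Posterior mean contrasts (differences, odds ratios, incidence rate ratios) between treatment groups will be reported together with 95% credible intervals". Both stand under the subheading for secondary efficacy endpoints.
- **Primary outcome:** the posterior of each proportional odds ratio (POR) "will be estimated using Markov Chain Monte Carlo techniques and the mean and 95% credible interval reported". The prior here is not vague. It is a "neutral informative prior distribution on the treatment effect where the variance will be chosen to only make extreme results highly unlikely".

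The serious adverse event paragraph of the same section compares arms by incidence rate ratio with a 95% credible interval, and names neither a point summary nor a prior. Section 3.5 lists the safety outcomes (stroke, myocardial infarction, ischaemic bowel, gastrointestinal perforation, severe neutropenia and others) as item viii of the secondary endpoints. The efficacy trigger in section 9.4 is a posterior probability: "at least an 84% probability of the proportional odds ratio exceeding 1.1".

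**The concern.** A ratio has a right-skewed posterior, so its mean lies above the exponentiated mean of the log ratio, and above the median when the log-scale posterior is roughly symmetric. The summary also depends on which arm is the numerator: with balanced data, the mean of the ratio and the mean of its inverse both exceed 1.

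With ample data this is cosmetic. With very few events and a vague prior, the likelihood hardly limits the upper tail, and the reported mean becomes a statement about the prior width. The listed safety outcomes include some likely to be sparse, and the arms may be small: section 9 expects a mean of 120 (hypoinflammatory) or 82 (hyperinflammatory) per intervention, with a first analysis at 80. What is at stake is how safety results read in the final report of each intervention. Balanced data could carry a point estimate that suggests several-fold harm.

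**Working it through.** The plan states no figure to reproduce. The check is what the stated summary would return.

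**Inputs from the protocol.** 80 per arm at the first analysis (240/3, section 9.4); caps of 504 and 529; logistic model for binary outcomes; efficacy trigger on a POR of 1.1 at 84%.

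**Assumptions, because the protocol gives no values.** Normal prior on the log odds ratio with SD 10, 2.5 or 1; normal prior on the intercept with SD 10; event rates of 1%, 2% and 5%; sum of cubed category probabilities for the primary scale of 0.02 to 0.20.

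**1. Sparse binary outcomes.** Posterior computed on a grid for a two-arm logistic model, 80 per arm:

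| Events (treated v control) | Prior SD | Mean OR | Median OR |
|---|---|---|---|
| 1 v 1 | 10 | 6.7 | just under 1 |
| 1 v 1 | 2.5 | 2.6 | just under 1 |
| 1 v 1 | 1 | 1.4 | 0.98 |
| 2 v 1 | 10 | 13.3 | 2.2 |
| 2 v 1 | 2.5 | 4.3 | 1.85 |
| 2 v 0 | 10 | over one billion | about 122 |
| 2 v 0 | 2.5 | 43 | 7.0 |
| 2 v 0 | 1 | 2.8 | 2.0 |
| 5 v 5 | 10 | 1.26 | 1.0 |
| 5 v 5 | 2.5 | 1.23 | 1.0 |
| 10 v 10 | 10 | 1.12 | 1.0 |

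For 1 v 1 at SD 2.5 to 10 the median lies at about 0.92 to 0.96. It falls slightly below 1 because this prior is wider for the treated arm's log odds than for the control arm's. The mean moves from 2.6 to 6.7 with the prior alone, while the median hardly moves. For 2 v 0 both depend on the prior.

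**2. Rate ratios.** With near-flat gamma priors, t treated and c control events and equal exposure, E[IRR] = t/(c − 1), against a raw ratio of t/c. The inflation is c/(c − 1): 2.0 at c = 2, 1.5 at c = 3, 1.25 at c = 5, 1.11 at c = 10. In the flat limit there is no finite mean at c = 0 or 1.

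**3. How often the control arm is that sparse.** P(c ≤ 1) = (1 − p)^n + np(1 − p)^(n−1):

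| Assumed rate | n = 80 | n = 120 | n = 240 | n = 504 |
|---|---|---|---|---|
| 1% | 81% | 66% | 31% | 4% |
| 2% | 52% | 31% | 5% | under 0.1% |
| 5% | 9% | 2% | under 0.1% | under 0.1% |

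**4. Primary POR.** With a near-normal log-scale posterior, mean/median = exp(SE²/2), and Whitehead's approximation gives SE = √[6 / (n(1 − Σp³))], ignoring the prior. For n = 80 and Σp³ = 0.07, SE = √(6/(80 × 0.93)) = 0.284 and the ratio is exp(0.0403) = 1.041. Over Σp³ of 0.02 to 0.20 the excess is about 4 to 5% at n = 80, 2.6 to 3.2% at 120, 1.3 to 1.6% at 240, and 0.6 to 0.7% at 504 to 529. A result exactly at the efficacy trigger at n = 80 has median exp(ln 1.1 + 0.994 × 0.284) = 1.46 and mean 1.46 × 1.041 = 1.52. The 95% interval runs from about 0.84 to 2.55.

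**The case against.** - **Scope.** The vague-prior and posterior-mean sentences sit under secondary efficacy endpoints, and the adverse event paragraph names no point summary. A reader might infer that the protocol explicitly fixes this method for safety events; it does not. The inference is still fair: safety outcomes are listed as secondary endpoints, and serious adverse events are the only outcome for which an incidence rate ratio is otherwise named.
- **Wording.** Posterior mean contrasts could be means on the log scale, exponentiated for reporting, which would remove most of the shift. The protocol does not say so, and the primary-outcome sentence, which takes the mean of the POR posterior, reads the other way.
- **SAP detail.** Prior scale and sparse-event handling commonly belong in the SAP, and the protocol defers full detail there. That stands for the prior scale. The choices of posterior mean and vague prior, however, are written into the protocol, and an SAP that follows them inherits the problem.
- **Reader protection.** Every ratio comes with a 95% credible interval, and serious adverse events are tabulated by arm. A reader who sees 1 v 1 beside a very wide interval is unlikely to be badly misled. This lowers the harm but does not make the point estimate useful.
- **Primary outcome.** A reader might infer that the primary effect is materially overstated at early stops, or that stopping is affected. The documents do not support either. The shift is small beside the interval, the primary prior is not vague, and the triggers are posterior probabilities, which do not depend on the point summary. The posterior mean is also a standard Bayesian summary.

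**Conclusion.** The point holds as a reporting matter for sparse safety outcomes. If the stated method is applied to them, a posterior mean ratio with 0 to 2 control-arm events mainly reflects the prior width: about 2.6 to 6.7 for 1 v 1 events, and 43 to over one billion for 2 v 0, at 80 per arm with prior SD 2.5 to 10. These figures illustrate assumed priors and counts; the plan does not fix them. It would go too far to call safety ratios in general meaningless: by 5 v 5 events the mean odds ratio is about 1.2 to 1.3, and by 10 v 10 about 1.1.

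For the primary POR the effect is about 4% at 80 per arm and under 1% at the caps. Stopping decisions, power and type I error are unaffected.

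**What to change.** In Protocol section 9.6, and in the SAP to match:

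1. For every ratio measure (POR, odds ratio, incidence rate ratio), report the posterior median, or the exponentiated posterior mean of the log ratio, with the 95% credible interval. Differences can stay as posterior means.
2. For sparse binary and count safety outcomes, replace the vague prior with a weakly informative prior on the log ratio, for example SD 1 to 2.5, with its scale stated in advance.
3. Say explicitly that these rules cover the safety outcomes of section 3.5 and serious adverse events.

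Both of the first two changes are needed. For 2 v 0 events, the median under SD 10 is still about 122, so the median alone does not cure a zero cell. Under SD 2.5 the mean is still 43 against a median of 7.0, so the prior alone does not cure the mean.

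The cost is a few lines of wording and a trivial change in code. The downside is mild shrinkage of rare-event ratios towards 1. It should be settled before the first final analysis of any intervention.

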10. REGULATORY, ETHICAL AND LEGAL ISSUES

10.1 Declaration of Helsinki

The investigator will ensure that this study is conducted in full conformity with the current revision of the Declaration of Helsinki.

10.2 Good Clinical Practice

The study will be conducted in accordance with the guidelines laid down by the International Conference on Harmonisation for Good Clinical Practice (ICH GCP E6 guidelines).

10.3 Ethics Committee Approval

(i) Initial Approval

Prior to the shipment of IMP (where applicable)/device and the enrolment of participants, the EC must provide written approval of the conduct of the study at named sites, the protocol and any amendments, the Participant Information Sheet and Consent Form, any other written information that will be provided to the participants, and any advertisements that will be used.

(ii) **Approval of Amendments**

Proposed amendments to the protocol and aforementioned documents must be submitted to the relevant EC for approval. Amendments requiring EC approval may be implemented only after a copy of the EC's approval letter has been obtained. If, after an adaptive analysis an intervention is deemed harmful or futile, as determined by the DMC, removal of these interventions may be implemented without submitting an amendment to the Sponsor, regulatory authority or EC. An official letter from the Data Monitoring Committee (DMC) will be submitted to the Sponsor, regulatory authority and EC detailing the decision soon as possible after implementation. Any additional interventions will always be submitted to the Sponsor, regulatory authority and EC for approval prior to implementation.

Further details can be found in the region-specific appendices.

End of Trial Notification

The EC and regulatory authority will be informed about the end of the trial, within the required timelines.

Confidential Page 34 of 48

London

10.4 Regulatory Authority Approval

The study will be performed in compliance with each country's regulatory requirements. Clinical Trial Authorisation from the appropriate Regulatory Authorities must be sought/obtained (as applicable to local country regulations) prior to the start of the study. In addition, the Regulatory Authorities must approve amendments prior to their implementation (as instructed by the Sponsor), receive SUSAR reports and annual safety updates, and be notified of the end of the trial.

10.5 Non-Compliance and Serious Breaches

All protocol deviations and protocol violations will be reported via the eCRF/CRF and reviewed by the Chief Investigator and / or trial manager / delegate and reported to the ICTU Head of QA on a monthly basis. Protocol violations will be reported to the Sponsor.

An assessment of whether the protocol deviation/violation constitutes a serious breach will be made. A serious breach is defined in the RSA.

The Sponsor will be notified within 24 hours of identifying a likely Serious Breach. If a decision is made that the incident constitutes a Serious Breach, this will be reported to the regulatory authorities in accordance with local regulatory requirements.

10.6 Insurance and Indemnity and Sponsor

The Sponsor has civil liability insurance, which covers this study in all participating countries. Imperial College London holds negligent harm and non-negligent harm insurance policies which apply to this study.

Imperial College London will act as the main Sponsor for this trial. Delegated responsibilities will be assigned to the sites taking part in the trial. Other delegated responsibilities will be documented as required in regional appendices and the relevant contracts.

10.7 Trial Registration

The study will be registered on the ISRCTN registry.

10.8 Informed Consent

The consent process will be conducted as per local regulatory authority/EC requirements and recommendations. If the patient has capacity, they will always be approached to provide their informed consent. Eligible patients for this trial will be critically ill. As such, they may be sedated for comfort, safety and to facilitate standard life saving ICU procedures, thus where permitted by the local regulatory authorities a deferred/delayed consent model can be used.

The consent process is detailed further in the region-specific appendices.

10.9 Participant Confidentiality

The investigator must ensure that the participant's confidentiality is maintained. On the CRF or other documents submitted to the Sponsors, participants will be identified by a participant ID number only. Documents that are not submitted to the Sponsor (e.g., signed informed consent form) should be kept in a strictly confidential file by the investigator.

Confidential Page 35 of 48

The investigator shall permit direct access to participants' records and source documents for the purposes of monitoring, auditing, or inspection by the Sponsor, authorised representatives of the Sponsor, Regulatory Authorities and ECs.

10.10 Data Protection and Participant Confidentiality

The investigators and study site staff will comply with the requirements of local Data Protection laws concerning the collection, storage, processing and disclosure of personal information.

This is detailed further in the region-specific appendices.

10.11 End of Trial

The trial is designed as a platform allowing for the continued evaluation of interventions for critically ill patients. The platform allows for the trial to be potentially perpetual, with multiple interventions that can be evaluated at any one time and over time. Frequent adaptive analyses are conducted to determine whether an intervention being studied should continue or cease due to efficacy or futility.

The trial will continue unless the ITSC agrees that one or more of the following situations apply:

- There is insufficient funding to support further recruitment to the platform as a whole and no reasonable prospect of additional support being obtained.
- New information makes it inappropriate to continue to randomise to any of the current interventions and this also makes it inappropriate to remain open to pursue new interventions for investigation.

10.12 Study Documentation and Data Storage

The investigator must retain essential documents until notified by the Sponsor, and for at least 10 years after study completion. Participant files and other source data (including copies of protocols, CRFs, original reports of test results, IMP dispensing logs, correspondence, records of informed consent, and other documents pertaining to the conduct of the study) must be retained. Documents should be stored in such a way that they can be accessed/data retrieved at a later date. Consideration should be given to security and environmental risks.

[figure not shown]
No study document will be destroyed without prior written agreement between the Sponsor and the investigator. Should the investigator wish to assign the study records to another party or move them to another location, written agreement must be obtained from the Sponsor.

11. DATA MANAGEMENT

11.1 Source Data

Source documents include original documents related to the trial, to medical treatment and to the history of the participant, and adequate source documentation must be maintained to

Confidential Page 36 of 48

allow reliable verification and validation of the trial data. What constitutes the source data for this trial will be outlined in the Source Data agreement.

11.2 Language

CRFs will be in an appropriate language for the regions in which the study is conducted Generic names for concomitant medications should be recorded in the CRF wherever possible. All written material to be used by participants must use vocabulary that is clearly understood and be in the language appropriate for the study site.

11.3 Database

Trial data will be collected on an electronic case report form (eCRF). Data will be entered via web-based database through electronic data capture (EDC). The database used to capture this information is the OpenClinica database. Data is entered into the database by the site team. The database will raise automatic queries and allow manual queries to also be raised which will be checked and validated by the Trial Manager and Monitor. All data, changes to data and query resolution will be included in an audit trail including dates. Specific instructions on how to enter data including drug naming and deal with queries are detailed in the eCRF completion guide. Automated Randomisation will be carried out using the OpenClinica system in accordance with ICTU specific SOPs.

Adverse events will be captured in the eCRF and all Serious Adverse Events will require sign off by the Principal Investigator at the site.

Exceptions to this will be detailed in the RSA.

